OVERALL IMPACT, SIGNIFICANCE, INVESTIGATOR(S) & INNOVATION: *inclusion/exclusion criteria not in grant (R1&R2).* We apologize for placing too much of that info in Human Subjects. It is now in section D.2 (and Human Subjects [1.a.]) *Unclear how nonadherence due to smartphone service loss will be handled (R1):* In our feasibility trials we observed high BP monitoring adherence via phone app (~88%), nonadherence tended to occur when cellular service was disrupted. We budgeted for 40% to receive a smart phone or data package to cover phone or service loss during the trial (in D.4.) *Justify relatively limited age range (21-59 yrs) (R1):* We are recruiting AAs from a federally qualified health center (FQHC) with sole diagnosis of HTN (n=2,619; mean age ~45.3 yrs). Majority of those ≥ 60 had multiple comorbidities & JNC8 BP control goals differ for patients <60 vs ≥60. *Concern PI may not have time (25%FTE) to devote to project (R1):* Within 2 mos of start date for this grant, [name] will be covered 50% FTE on grants (R21 & RO1 will have expired; see bio). He has a long track record of running successful concurrent trials. An experienced full time project manager has been added, [name]. *Consider adding someone with usability testing background (R1):* [name] is a consultant with expertise in user centered, iterative design in web/app programs including use of various usability evaluation tactics (e.g., expert heuristic & end user think aloud evals, questionnaires; see bio & letter). *SMASH not highly innovative, been used in other patient groups(R1):* Our patient centered design revealed significant heterogeneity of influence of cultural heritage/acclimation and numeracy of chronic diseases (single vs multi-morbidities) upon MA and other health behaviors within & across ethnic groups. The mHealth program tailored to Hispanics is not culturally attuned for AAs. Our mHealth work with AA renal transplant patients with HTN, diabetes, etc. led to efforts to address poor MA before multi-morbidities develop. Our long-term goal is to prevent common events (e.g., stroke, heart attack) & slow progression of common comorbidities (e.g., chronic kidney disease, diabetes) due to uncontrolled HTN. SMASH for transplant patients required ~2 years of changes to become salient to AAs with solely uncontrolled HTN. We found those with only HTN often have greater MA problems (in C.1.3) & to be more challenging to establish sustained regimen adherence compared to HTNs with multi-morbidities. Experiences during trials & post trial interviews led to an iterative process of identifying highly salient motivational factors (values, beliefs, goals) not needed with multi-morbidity transplant patients (in C.1.5.) Others have observed similar challenges with single vs multi-morbidity HTN patients (in A.2.) This program (nor any earlier iteration) has not been nor is being tested using a fully powered RCT, much less within a low-income population & health system (i.e., FQHC). *No focus on med nonadherence (MNA) mechanisms besides self-motivation or how other diseases & meds affect HTN MA; no lit review on comorbidities(R2):* We clarified HTNs with comorbidities aren't recruited (in D.2.) Exploratory analyses of MNA mechanisms now include med side effects, stress, depression symptoms, etc. (in D.10.) We added diabetes /CVD risk factor changes (e.g., TC, HgA1c) as exploratory outcomes. Recent trials show some newer HTN meds lower or at least do not increase these risk factors (in A.2.) **APPROACH & ENVIRONMENT:** *Limited description of clinics (R1):* 7 of 8 clinics have similar numbers of AAs with uncontrolled HTN and numbers of primary providers (MD, PA, NP; M=2.4). Lead site has 7.3 providers & generates ~45% of patient encounters (in Facilities & Resources). Clinic (=cluster) in our cluster RCT design will be a random effect in the analytic model & account for clinic site differences (in D.10). *More details on SMASH focus group protocol stratification process (R1):* We will identify 2 groups: 16 MA responders & 16 partial/nonresponders stratified by clinic, age & sex. We will run 3-4 focus groups separately by group classification (in D.7.) *Measures of numeracy, usability & project evaluation needed; SMASH & control condition descriptions a bit vague (R1):* We added measures (in D.6.) & reworded SMASH & SC protocols for clarity (in D5-7.) *No model to guide analytic approach; how will data be integrated to provide cohesive story (R1):* We clarified in D.10 our conceptual model is built upon Self-Determination Theory with competence & autonomous motivation as primary MA mediators. We now include socio-demographic (e.g., age, income) & biobehavioral (e.g., med side effects, stress, sleep quality, etc.) factors as potential moderators & mediators of MA. Those results will guide an integrated causal model using structural equation modeling that will identify key active ingredients of SMASH to guide future refinements.

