A.4. Therapeutic Inertia and Uncontrolled HTN: Therapeutic inertia, the failure of clinicians to appropriately intensify therapy in a timely manner, explains, in part, why among adherent patients, HTN often remains poorly controlled.⁶⁹⁻⁷² Although therapeutic inertia is a multifactorial problem, provider unawareness of best practice guidelines is a major culprit.⁷¹⁻⁷⁴ Okonofua, et al.,⁷² monitored for 12 months 7,253 patients with uncontrolled HTN who attended ≥4 clinic visits from 44 primary practice sites primarily in SC. Med changes occurred on only 13% of the visits at which patients exhibited uncontrolled HTN. Additionally, lack of real-time data as to HTNs' BPs at home and their degree of MNA means important medical decisions are often delayed until the next clinic visit that might be weeks or even months away. Thus, the SMASH program includes a practitioner component to reduce therapeutic inertia and follow JNC8 treatment guidelines (see D.5.b).

A.5. RCT BP Control Efficacy Gaps: A number of interventions have addressed MNA among HTN

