D.1. Design and Randomization: Subjects will be drawn from Fetter Health Care Network (FHCN). It is the sole FQHC center in the 4-county area (8 clinics) and provides ~60% of routine AA healthcare in the 4 county area.¹⁰⁷ A support letter from the FQHC network is included. EMR files indicated they have ~2,619 AAs (21-59 yrs old; mean age=45.3yrs) with sole diagnosis of uncontrolled HTN. We will use the 8 practice sites in a 2 arm RCT design (n=192) with clinic as unit of randomization and patient as unit of analysis. All primary healthcare providers across the 8 clinics have agreed to participate if selected. Each clinic has a minimum of 2 primary providers (at least 1 MD and 1 or more NPs and/or PAs per clinic). Thus, 2 providers per site will be recruited. Each will have 12 of their patients recruited (24 per clinic). Given our ~90% participation rate in previous FQHC studies^{25,108,109} and 93% SMASH participation rate, we anticipate no recruitment problems. The Medical University of South Carolina Family Medicine and Internal Medicine clinic population will be an additional recruitment resource if needed.

D.2. Participants: With consideration of the relevant biological variable of gender, we will recruit 192 AA 21-59 yr old uncontrolled HTNs with equal numbers of males and females that meet the following inclusion/ exclusion criteria: 1) SBP ≥ 140 mmHg on most recent clinic visit over last 12 mos and at BP screening and recruitment visits; 2) MPR < 0.85 over last 3 mos; 3) 24-hour SBP ≥ 130 mmHg (HTN cutoff) to help rule out white coat HTN.^{76,110} SBP used as selection variable since most AA HTNs < 60 have systolic or combination systolic/ diastolic HTN and for most patients, controlling SBP also results in DBP control;^{27,111,112} 4) no other known chronic diseases (e.g., diabetes, chronic kidney disease (GFR < 50 ml/1.73 m²/min), cancer, renal dialysis, heart attack, coronary artery bypass, arterial stent, substance abuse (e.g., > 21 drinks/week), psychiatric illness, Beck Depression Inventory¹¹³⁻¹¹⁵ > 13 , able to speak, hear and understand English; take own BP and meds; 6) owns smart phone with current data plan; 7) primary care MD's assent patient able to participate and 8) no planned pregnancy or vulnerable population (e.g., pregnant or nursing women, prisoners).

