D.7. Post-Trial Follow-up Focus Groups: Focus groups will be run after the final follow-up evaluations by Drs. [name], [name] & [name]. To help ensure robust and unbiased results, purposive sampling will be used to recruit 32 SMASHers based upon MA, termed responders (MA score >.90) or non/partial responders (MA score <.90) based upon their cumulative adherence score (MedMinder 6 mo score & MPR level across follow-up). Groups will also be stratified by sex, age group (<40; >40) and practice site (4 per site). The 16 subjects from each group will be divided into groups of 4 to 5 (i.e., 3-4 focus groups). A semi-structured interview guide with topic area probes will cover expectations, experiences, adherence, motivation, SMASK system usability and overall satisfaction. We will explore suggestions for improving the SMASK app content and features, tray/BP device usage, quality of SMS, and possible future use of motivational interviewing booster calls, etc., especially among non/partial responders.

The 8 SMASH primary providers and 4 nurse managers from the 4 SMASH sites will engage in a focus group (1 for providers; 1 for nurses). We will assess attitudes, beliefs, aids/barriers to use, feedback on retention, impact on therapeutic inertia and other practice considerations. Focus groups will be audio recorded and field notes written to note any reflexive findings and initial impressions. Recordings will be professionally transcribed, verified for accuracy and imported to NVivo 11.0 (QSR International PTY, Doncaster, Victoria Australia) for analysis.

D.8. Sample Size Justification & Power Calculations: For AIM 1: Sample size/power calculations were based on two-sided

Table 3. Outcome Variables & Measurements/Instruments Used		
Outcome Variables	Measurements/Instruments Used (Cronbach's α)	Time points
Primary Outcomes		
MA	MedMinder (time-stamped) primary measure.	Daily for 6 mos
	Self-report (Morisky Medication Adherence Scale [76- 83] (Appx.1)).	Baseline,3,6,12,18 mos
	Med Possession Ratio [MPR] (Appx.30).	
BP	Resting SBP (Appx.5).	Baseline,3,6,12,18 mos
Secondary Outcomes		
Therapeutic Inertia	Provider adherence to JNC8 goals: Timely med changes (date of med change following MA & BP feedback).	weekly SMASH reports (SMASHers) and from clinic visits for all subjects
Ambulatory BP	24-hr Ambulatory BP with Spacelabs 90207 (Appx.22).	Baseline,3,6,12,18 mos

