
For AIMS 2: secondary outcomes (changes in SDT constructs [i.e., competence & autonomous motivation], % reaching & sustaining 24-hr BP control [<130/80 mmHg], therapeutic inertia (i.e., % making med change in patient's EHR & script delivery to patient or pharmacy within 24 hours of subject's clinic visit and/or receiving BP info report)⁷² and **AIM 3: exploratory outcomes** (cost effectiveness; changes in TC, LDL, HgA1c, blood glucose) in the intent-to-treat sample, we have 80% power to detect a difference of 0.53 sd between the 2 groups assuming $\alpha = 0.05$ (Type I error rate), two sided; independent sample t-test comparison of means; equality of variance between groups. For 24-hour BP, we will have > 85% power to detect a 30% difference in % reaching 24-hr BP control between groups. Our 24-hr BP data from a subgroup (N=12) of FQHC AAs in the feasibility trial found 85% of the SMASH group vs 25% of the SC group achieved 24-hr BP control at 6 mos.

D.9. Data Management & Quality Control: Quality control checks of anthropometrics/BP evaluations & 24-hr BP protocol delivery will be run on random selection of 10% of subjects per mo & protocol retraining conducted as needed. Questionnaire data will be directly captured via REDCap (HIPAA compliant, web-based app) & overseen by [name] and [name]. Clinic data (e.g., anthropometrics, BP) & EMR derived data (e.g. TC, HgA1C) will be double entered with discrepancies resolved by [name]. Data will be reviewed on twice-monthly basis. Outlying, inconsistent data values, as well as missing data, will be targets of the data quality review. Issues will be communicated to Drs. [name], [name] and [name] for resolution.

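### The 80% power at 0.53 SD stated for therapeutic inertia does not follow from D.8's own clinic ICC of 0.04, and makes no stated allowance for clustering by provider, with 8 providers per arm

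*Combined protocol and SAP*

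**What the plan says.** D.1 sets up a cluster design "with clinic as unit of randomization and patient as unit of analysis". On providers it says: "Thus, 2 providers per site will be recruited. Each will have 12 of their patients recruited (24 per clinic". With 4 clinics per arm this is 8 providers per arm. D.7 gives the same count: "The 8 SMASH primary providers and 4 nurse managers from the 4 SMASH sites will engage in a focus group".

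D.8 (Aims 2 and 3) gives a single figure for a list of outcomes that includes therapeutic inertia: "we have 80% power to detect a difference of 0.53 sd between the 2 groups". The stated basis is "Type I error rate), two sided; independent sample t-test comparison of means; equality of variance between groups". No ICC, variance inflation factor or number of providers is attached to it. Inertia is defined there as a percentage: a medication change made and the script delivered within 24 hours of a visit or report.

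The only clustering ICC adopted in D.8 is 0.04, in the Aim 1 paragraph. It comes from tray-based adherence and systolic pressure in the feasibility trials, and is applied with 22 evaluated patients per clinic and 4 clinics per arm (176 in all, raised to 192 for attrition).

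Section A.4 describes therapeutic inertia as "the failure of clinicians to appropriately intensify therapy in a timely manner". D.10 models practice site as a random effect, says this covers clustering by site or physician, and specifies no separate provider term.

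**The concern.** Two things do not fit together. First, the power statement for this outcome carries no clustering assumption, although clinics are randomised and the same section adopts an ICC for the primary outcomes. Second, inertia is recorded on patients, but the act being counted is mostly the provider's. Twelve patients of one provider share that provider's habits, so they carry less information than twelve independent patients.

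Inertia is a named secondary outcome and the reason for the provider component of SMASH. If its power is overstated, a null result could be read as evidence that the reports do not change prescribing, when the trial may have had little chance of showing that they do.

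**Working it through.** **Inputs from the documents.** Difference 0.53 SD; two-sided alpha 0.05; 4 clinics and 8 providers per arm; 88 evaluated patients per arm (22 per clinic, 11 per provider) or 96 recruited (24 and 12); clinic ICC 0.04. **Assumed:** any provider ICC, since the documents give none.

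**Formulas.** Design effect DE; effective patients per arm n_eff = n / DE; power = Φ(0.53 × √(n_eff/2) − 1.96); difference detectable with 80% power = 2.80 × √(2/n_eff). These use a normal reference unless stated.

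**Step 1. The plan's figure.** 80% power at 0.53 SD needs 56 (normal) or 57 (t) independent patients per arm. An unadjusted t-test would have 94% power with 88 per arm and 96% with 96. So the 0.53 SD appears to contain some allowance:
- 88/57 = 1.54 and 88/56 = 1.57. Implied clinic ICC = (DE − 1)/21 = 0.026 to 0.027.
- 96/57 = 1.68 and 96/56 = 1.71. Implied clinic ICC = (DE − 1)/23 = 0.030 to 0.031.

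With 96 per arm and ICC 0.03, the t-test gives 80.0%. The figure can therefore be recovered, but only at an ICC that D.8 does not state for it.

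**Step 2. D.8's own clinic ICC of 0.04, no extra provider effect.**

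| n per arm | DE | n_eff | Power, normal | Power, t | Power, 6 df | Detectable at 80% |
|---|---|---|---|---|---|---|
| 88 | 1 + 21 × 0.04 = 1.84 | 47.8 | 74% | 73% | 58% | 0.57 SD |
| 96 | 1 + 23 × 0.04 = 1.92 | 50.0 | 75.5% | 75% | 60% | 0.56 SD |

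The 6 degrees of freedom are 8 clinics minus 2 arms.

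**Step 3. Provider clustering, as an assumption.** For 88 per arm, DE = 1 + 10 × ICC_p with provider clustering alone, and 1 + 21 × 0.04 + 10 × ICC_p with the clinic ICC added. Here ICC_p is the share of variance due to providers over and above clinics.

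| Provider ICC (assumed) | DE, provider only | Power | DE, with clinic 0.04 | Power |
|---|---|---|---|---|
| 0.03 | 1.30 | 87% | 2.14 | 67% |
| 0.05 | 1.50 | 82% | 2.34 | 63% |
| 0.1 | 2.00 | 70% | 2.84 | 55% |
| 0.2 | 3.00 | 53% | 3.84 | 43% |
| 0.3 | 4.00 | 42% | 4.84 | 36% |
| 0.4 | 5.00 | 35% | 5.84 | 31% |

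With 96 per arm the results are 0 to 2 points higher (provider only: 89% at 0.03 and 84% at 0.05; with clinic: 65% at 0.05 and 31% at 0.4).

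**Step 4. Break-even.** With no clinic effect, 80% holds up to a provider ICC of (88/57 − 1)/10 = 0.054, or (96/56 − 1)/11 = 0.065 at most. With the clinic ICC at 0.04, power is below 80% before any provider effect is added.

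**The case against.** A reader might infer that power for inertia is 35 to 70%. That range needs a provider ICC of 0.1 to 0.4, which no document supplies and which begins above the break-even of about 0.055. At 0.03 to 0.05 with no clinic effect, power is 82 to 89% and the stated figure stands. Section A.4 also calls inertia multifactorial, and the outcome requires script delivery, so patient and pharmacy factors add variation within a provider. This objection holds: the low range is a sensitivity result, not a finding.

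A reader might also infer that the plan treated patients as independent. It did not simply do so, because an unadjusted test would have 94 to 96% power. D.8 considers ICCs from 0.0 to 0.05 for Aim 1, and 0.03 lies inside that range. But the value D.8 adopts and calls conservative is 0.04, and the 0.53 SD does not match it.

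Third, a reader might infer that limiting recruitment to two providers per clinic is the fault, since "All primary healthcare providers across the 8 clinics have agreed to participate if selected". The documents do not support that. D.1 ties two to the minimum that every clinic has. The total of about 24 is inferred (7 × 2.4 + 7.3 = 24.1) from a mean and from a fractional count: "Lead site has 7.3 providers & generates ~45% of patient encounters". Most of the gain would fall in one site and so in one arm. Spreading the same patients over all providers adds about 6 to 8 points with provider clustering alone, and about 4 to 5 points at provider ICC 0.1 to 0.2 with the clinic ICC included. It does not reach 80% at any provider ICC from 0.1 to 0.4.

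Finally, the site random effect in D.10 is meant to cover clustering by physician. That is a partial acknowledgement, but it does not separate two providers in one clinic.

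**Conclusion.** The concern holds in a limited form. On D.8's own clinic ICC of 0.04, power at 0.53 SD is about 73 to 76%, not 80%, and 58 to 60% if the test uses 6 clinic-level degrees of freedom. The shortfall on the normal reference is modest: 0.56 to 0.57 SD detectable instead of 0.53. It rests on carrying 0.04 over to this outcome, since the plan gives inertia no ICC of its own.

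Beyond that, provider clustering can only lower power further, and 8 providers per arm make it matter. How far is unknown: about 63% down to 31% for assumed provider ICCs of 0.05 to 0.4 added to the clinic ICC. The primary-endpoint calculation is a separate one and is not at issue here.

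**What to change.** In D.8, take therapeutic inertia out of the blanket statement of 80% at 0.53 SD. Restate its power, or its detectable difference, using the clinic ICC of 0.04 and a stated range of provider ICCs for 8 providers per arm, and say whether the reference distribution allows for 8 clinics. Preferably give it as a difference in percentages, because the outcome is a percentage. As a guide, the SD of a yes/no outcome is at most 0.5, so 0.53 SD is at most 0.53 × 0.5 = 26.5 percentage points and 0.57 SD at most 28.5.

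In D.10, for this Aim 2 outcome, add provider nested in clinic to the model.

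The cost is a less favourable stated figure and one more variance component, to be estimated from 16 providers. No change to recruitment, to the number of providers or to the sample size is proposed.

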AIM 2) Secondary Outcomes: a) % provider adherence to JNC8 guidelines measured by timing of med changes; b) % meeting 24-hr BP control (BP<130/80 mmHg) and c) increases in self-determination theory constructs (i.e., competence & autonomous motivation).

AIM 3) Exploratory Outcomes: a) moderators (e.g., gender, age, income, etc.) and mediators (e.g., competence, autonomous motivation, perceived disease severity, med side effects, depressive symptoms, etc.) of MA and BP control; b) cost effectiveness and c) physical risk factor changes (total cholesterol, LDL, blood glucose, HgA1c).

AIM 4) SMASH Refinement: A mixed methods approach will be used including post-study questionnaires (e.g., patient/provider satisfaction, usability scales, etc.) and focus groups of 5-6 people with SMASH providers (n≈12) and SMASH subjects (16 responders and 16 partial/non-responders) will assess program acceptability, usability, salience and aids/barriers to sustainability. Data from the RCT and post trial multi-method evaluations will be triangulated to further optimize SMASH and prepare for a multi-site effectiveness RCT.

Our **long-term objective** is to develop effective sustainable mHealth programs for HTN and other chronic diseases. Dissemination of such programs will help reduce burden of HTN associated health disparities.

A. SIGNIFICANCE

A.1. HTN and AAs: HTN, the most commonly diagnosed chronic disease in the US, is an independent risk factor for stroke, renal failure, and CVD events.^{1,2} Unfortunately, racial/ethnic disparities persist with AAs exhibiting earlier onset, higher prevalence rates than all other ethnic groups (~39% vs 19-28%) and higher rates of uncontrolled HTN(54-70 %) than Whites(47-54%),^{3-5,27-30} Risk factors for poor control of HTN include nonwhite ethnicity, poorer socioeconomic status, and residence in rural southeastern United States.^{29,30} These risk factors are all prevalent in South Carolina,³⁰ and support need for culturally sensitive BP control programs for this population at significant risk for stroke, chronic kidney disease, type two diabetes and CVD events.³¹⁻³⁶

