D.3.b. MNA Identification Phase: Subjects will be shown how MedMinder™ works and demonstrate proficiency in loading and activating the device. They will be told their doctors will receive summary reports on their med intake patterns. The tray plugs into a standard 110v outlet, has 28 compartments allowing up to 4 dose times per day for 7 days, and is capable of providing escalating reminder signals (described in D.5.a). **Reminder functions will be disabled for the 1-month screening phase.** The nurse manager (or project manager, [name]) and subject will program the MedMinder for dosing times (example of subject's 24-hr MedMinder activity in Appx. 23). Subject will receive written and oral instructions on MA criteria (i.e., all meds taken within 180 min window centered on prescribed dosing time). SMASH app has auto call feature for TACHL service line for technical issues. Time and date stamped opening and closure of the tray's compartments are relayed via GSM wireless cellular transmitter/receiver to MedMinder™ server for processing. The encrypted data are sent to a HIPPA-compliant server database housed in the TACHL center. The MA formula will be used to calculate MA scores.^{22,23,52,121} (see Appx. 2) **Only subjects with MA score < 0.85 over the 4 week screening and whose subsequent resting and 24-hr SBP evaluations reconfirm uncontrolled HTN will be eligible for enrollment into the RCT.** [name] will randomly assign the 8 sites to either SMASH or

enhanced SC conditions.

D.4. Time Table (Table 2) Based on our SMASH trials, we will recruit 16 subjects/mo beginning mo 4 and finish recruiting by mo 15. We will provide a smart phone and/or service plan for ~40 SMASHers we project might lose phones or service plans during the trial.^{20,21,25,27} Post-trial data collection will finish in mo 34. Post study focus groups and subsequent qualitative analyses will end in mo 43. Table 2 presents a timetable for the study.

Activity	Month
Set-up	Mos 1-3
Recruitment	Mos 4-15
Intervention	Mos 5-22
Follow-up	Mos 16-34
Focus Groups	Mos 35-37
Statistical analyses	Mos 23-28
Prep. and Submission of Effectiveness RCT RO1	Mos 36-42
	Mos 43-48
Month	0 2 4 6 8 10 12 14 16 18 20 22 24 26 28 30 32 34 36 38 40 42 44 46 48
Year	1 2 3 4

D.5. SMASH Protocol:

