Cochran-Mantel-Haentzel chi-square tests of differences in % of patients being >0.90 med adherent and % of patients within JNC8 guidelines for BP control (<140/90 mmHg) at the 6 month visit (primary endpoint) between the two groups (SMASH; enhanced SC). Type I error rate was 0.05 (two-sided). Sample size was adjusted to account for the cluster randomization scheme, using variance inflation factor (VIF) method.¹⁴⁸ Power and sample size estimates were performed for within-clinic sample sizes of 22 subjects for 4 clinics per group, assuming ICCs ranging from 0.0 to 0.05. The ICC from our feasibility trials for primary outcomes of electronic med tray based MA and SBP was estimated at 0.04. For an ICC of 0.04 the proposed sample size of 22 per clinic and 4 clinics per group provides at least 90% power to detect a difference in the assumed 6-month MA/BP control rates between the 2 groups (difference of $\geq 30\%$ between SMASH and SC based on feasibility trials' results).^{22,23,25,26} For the proposed study, for calculation of the VIF we used the conservative absolute ICC value of .04 for a final sample size 176. We inflated that by 10% (N=192) to account for greater than expected attrition across the trial. Conservative estimates for expected MA (or BP control) proportions were used for power calculations; proportions observed in our SMASH feasibility studies were 89% vs. 0%, N=19 for MA based upon MedMinder^{22,23} and for resting SBP, an average of 90% vs. 10% for the three trials lasting 3 and 6 months and the recent 12-month follow-up (n=19,²² n= 22,²⁵ n= 24,²³ n=19,²²). For secondary continuous outcomes of 24-hr BP (and MPR derived MA scores) for longitudinal analyses [assuming 4 intervention time points (months 3, 6, 12, and 18), level of significance = 0.05 (two-tailed), correlation among repeated measures (ICC ≤ 0.5)], we will have 90% power to detect a 0.48 standardized effect size (i.e., Cohen's d effect size). A standardized effect size of 0.48 sd is equivalent to a raw effect size ranging from 2.4 to 4.3 mmHg (raw scale units) for difference in SBP change from baseline between the groups for a range of sd from 5.0 to 9.0 mmHg, based upon our SMASH feasibility data.^{22,23,25,26} For resting DBP based upon our SMASH findings, this equates to a difference of 1.3 to 3.3 mmHg assuming sd ranging from 2.0-5.0 mmHg. SMASH findings for the tray derived monthly MA scores revealed a difference in MA score changes between the groups from baseline to 3 month of 28% (sd=6.2).^{22,23} Assuming similar adherence in both groups through the 6-month trial, we will have at least 94% power to detect differences in adherence change scores as small as 10% (with sd up to 15).

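### The 8 clinics are assigned by an unrestricted draw, and the random clinic effect relied on for site differences models clustering but cannot remove a chance imbalance between the arms

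*Combined protocol and SAP*

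**What the plan says.** - **Assignment.** D.1 describes a two-arm trial "with clinic as unit of randomization and patient as unit of analysis". D.3.b says that a staff member "will randomly assign the 8 sites to either SMASH or" enhanced SC. The Human Subjects section (1.a) repeats that sites are randomly assigned and adds no method. Four clinics per arm is implied by D.7 and by D.8, which uses "within-clinic sample sizes of 22 subjects for 4 clinics per group, assuming ICCs ranging from 0.0 to 0.05".
- **Clinic size.** D.1 fixes recruitment at two providers per site: "Each will have 12 of their patients recruited (24 per clinic").
- **Clinic similarity.** The introduction to the revised application says "7 of 8 clinics have similar numbers of AAs with uncontrolled HTN and numbers of primary providers (MD, PA, NP; M=2.4"), and then "Lead site has 7.3 providers & generates ~45% of patient encounters". Blood pressure control, case mix and access to care are not reported by clinic.
- **Handling of site differences.** The same section answers a grant-review query about the clinics with "Clinic (=cluster) in our cluster RCT design will be a random effect in the analytic model & account for clinic site differences".
- **Analysis.** D.10 puts practice site as a random effect in the longitudinal GLMM/GEE-type model, where the stated purpose is clustering. The 6-month comparison is an unadjusted Cochran-Mantel-Haenszel test, followed by a logistic regression with no covariates listed. Neither has a stated clinic term. The first set of longitudinal models adjusts for the baseline value of the outcome. No clinic-level covariate is named.

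**The concern.** A random intercept for clinics nested within arm describes how much clinics vary. It has no information with which to separate a treatment effect from a difference in prognosis between the four clinics that drew SMASH and the four that drew SC. If the draw happens to put better-prognosis clinics in one arm, that difference stays in the estimate.

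With only 8 clusters such splits are common, and the one split drawn is the one the trial must defend. The statement in the introduction suggests that the matter is already dealt with. At the 6-month primary endpoint the protection it cites is not stated at all.

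**Working it through.** **1. The plan's own figures (D.8).** 22 × 8 = 176 before attrition, and 24 × 8 = 192 recruited. Variance inflation is 1 + 21 × 0.04 = 1.84, so the effective size per arm is 88/1.84 = 47.8. The arm rates behind the 30-point difference are not given. Normal-theory power is 93.6% at 40% v 10% and 84.6% at 65% v 35%, so the stated 90% or more is reproduced only for some rates.

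**2. What the random effect does.** Simulation with 8 clinics of 24, an imbalanced clinic trait and no true effect:

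| Analysis | Mean SMASH estimate | Mean SE |
|---|---|---|
| No clinic term | 0.203 | 0.146 |
| Random clinic intercept | 0.203 (largest gap 1e-15) | 0.211 |
| Trait as covariate | -0.001 | 0.166 |

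Binary example (assumed): a trait held by 4 clinics raises control from 35% to 50%, and the clinics with it split 3 to 1. The expected false difference is (3 × 50 + 35)/4 − (50 + 3 × 35)/4 = 46.25 − 38.75 = 7.5 points. The odds ratio averages 1.37 with plain logistic regression. It is the same with an exchangeable GEE (largest gap in the log odds ratio 3e-12), and is 1.01 with the trait as covariate.

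**3. How much imbalance a free draw allows.** There are C(8,4) = 70 splits. For a clinic factor with SD s, the variance of the arm difference over the splits is s²(1/4 + 1/4) = s²/2, so the root mean square is 0.71 s. Ranking the splits by summed squared standardised difference and keeping the best 42, over 4,000 simulated sets of 8 normally distributed clinic values:

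| Draw | RMS difference | Share of draws above 0.71 SD |
|---|---|---|
| All 70 splits | 0.71 SD | 36% |
| Best 42, one factor | 0.37 SD | under 1% |
| Best 42, two factors (each) | 0.48 SD | 16% |

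**4. On the outcome scale.** At ICC 0.04 the between-clinic SD is √(0.04·p(1−p)): 8.7 points at p = 0.25 and 10 points at p = 0.50. The 4 v 4 difference has that SD × √(2/4), or 6.1 to 7.1 points. A chance shift of 10 points or more then has probability of about 10% to 16%. This covers all between-clinic variation. Restriction removes only the part explained by the balanced factors.

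**5. Power with valid clinic-level inference (25% v 55% and ICC 0.04 assumed, 22 per clinic).** SE = √[(0.55 × 0.45 + 0.25 × 0.75) × 1.84/88] = √(0.435 × 1.84/88) = 0.0954. The noncentrality is 0.30/0.0954 = 3.15, and on 6 df (critical value 2.447) power is about 75%. By simulation, with the two factors explaining a quarter to half of clinic variance:
- t test on 6 df: about 73% to 75%, with or without the constraint.
- Test adjusted for both factors (4 df): about 64% to 69%.
- Permutation test within 42 splits: about 60% to 62%. Its smallest p is 2/42 = 0.048 and the next is 4/42 = 0.095, so it rejects only when the observed split is in the most extreme mirror pair.

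**6. The lead site.** It supplies 24/96 = 25% of whichever arm it joins. If its control rate differs from the others by 10, 20 or 30 points, the contrast moves by 2.5, 5 or 7.5 points under any allocation.

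**The case against.** The case for leaving the draw as it is has real substance.

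- **Random assignment is unbiased, and the clinic variance is already budgeted.** Both are true. The 6 to 7 points in step 4 is the same ICC component that D.8 inflates for, and a correct clinic-level standard error covers it. It is not an extra error. What remains is that the realised imbalance could be made smaller at little cost.
- **The clinics are alike.** A reader might infer from the lead-site figures that the eight clinics are unlike. The documents do not say so: seven of eight are similar in patient and provider numbers. That is similarity in size; similarity in prognosis is not reported. A.1 lists "poorer socioeconomic status, and residence in rural southeastern United States" among risk factors for poor control, but as general epidemiology. It does not say that these clinics differ from one another on either, so no rural/urban split of the eight can be assumed.
- **Adjustment is planned and can repair imbalance.** Partly right. A measured clinic trait entered as a covariate removed the false effect in step 2, so it would be wrong to say that nothing can be done later. But no clinic-level factor is named, and each one costs 1 of about 6 df. The baseline values of the two binary primary outcomes cannot help, because eligibility makes everyone uncontrolled and non-adherent at entry. Only the continuous levels, truncated by the entry criteria, carry information. Narrow eligibility does limit case-mix differences.
- **The sentence in the introduction answers grant review; D.10 is the operative text.** Fair. D.10 gives the correct purpose, clustering. The two statements still need to agree, and D.10 does not extend the term to the 6-month analyses.

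**Conclusion.** The point holds as a design improvement that should be made before the draw. The plan describes no restriction on assigning 8 clinics, and the random clinic effect cannot do what the introduction says of it. At 6 months it is not stated at all. Constrained randomisation would cut the typical arm difference in a clinic factor from 0.71 to about 0.37 SD (one factor) or 0.48 SD (two). The figure of 0.71 is exact. The other two come from simulation with normally distributed clinic values. The benefit to the outcome depends on how prognostic the chosen factors are, which the documents do not show.

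A reader might also infer that balancing would raise power, since the normal-theory formula at 25% v 55% gives 86%, 90% and 94% as the ICC falls from 0.04 to 0.03 and 0.02. That inference is not supported. It assumes that a quarter to half of clinic variance is explained, and it ignores the degrees of freedom for 8 clusters. With clinic-level inference, power is about 73% to 75% with or without the constraint. The gain is balance, credibility and slightly lower error variance. Nothing here shows the planned estimate to be biased.

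**What to change.** 1. In D.1 and D.3.b, state the assignment method. From the EMR extract that identified the 2,619 patients, tabulate one or two clinic-level prognostic factors, for example mean last SBP and one access measure. List the 70 splits, keep at least 42 (21 mirror pairs) with the smallest summed squared standardised difference, and draw one at random. Two strata of four would leave 36 splits (smallest permutation p 2/36 = 0.056) and pairing 16 (2/16 = 0.125), so a constrained list of 42 is preferable if a permutation test is kept as a sensitivity analysis.
2. Name the two participating providers at each site before the draw. This matters most at the lead site, where two are taken from about seven.
3. In D.10, specify clinic-level small-sample inference for the 6-month comparison (about 6 df). Do not make the permutation test primary. Prespecify which clinic-level covariate, if any, is adjusted for.
4. Reword the introduction so that the random effect accounts for clustering, not for site differences.
5. Add a sensitivity analysis without the lead site.

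Cost: a few hours of statistician time before the draw. The lead site stays unbalanced, each clinic-level covariate uses 1 of about 6 df, and no power gain can be claimed. If the draw has already been made, report the clinic-level factors by arm and prespecify at most one as a covariate.
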